6.3 Acoustic Pulse Thrombolysis Procedure, Treatments and Timing

6.3.1 Anticoagulation

All study subjects will continue on the anticoagulant medication initiated prior to enrollment in the trial. For those subjects receiving full dose anticoagulation with intravenous unfractionated heparin, their dose will be reduced to intermediate dose continuous infusion, target aPTT 40-60 seconds, during the APT Procedure. Subjects receiving anticoagulants other than unfractionated heparin (such as low molecular weight heparin, fondaparinux) prior to enrollment in the trial will not receive any additional intravenous heparin during the APT Procedure provided they received therapeutic doses of the anticoagulant.

Following the APT Procedure, subjects will be prescribed ongoing anticoagulation therapy of the physician's choice which will be recorded in the eCRF throughout the 12 month follow-up period.

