6.3.2 Timing of APT Procedure

The subject will have treatment with the APT Procedure started within 48 hours from the Screening/Baseline CTA evaluation.

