At 72 hours after the start of APT Procedure or at discharge from hospital, whichever comes first, all Adverse/VTE/Bleeding Events that occurred from Screening/Baseline will be recorded in the eCRF. Any events recorded will be followed to resolution.

Data Collected for Hospital Stay

From Admission through Discharge, intervals will be collected including the following:

1. Time from hospital admission to diagnosis of PE

2. Time from diagnostic CTA to start of APT procedure
3. Time of each aspect of the procedure: beginning (start of APT procedure), end (conclusion of APT procedure), assessment times, rate of infusion and total dose of r-tPA. If the APT procedure is restarted, collect beginning and end of APT Procedure, rate of infusion and total dose of r-tPA.
4. Time in each Level of Care (Level 0 and 1; Level 2; and/or Level 3) through discharge. Levels are defined according to National Framework Document.

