8 SAFETY REPORTING

8.1 Adverse Events

An adverse event (AE) is defined as any untoward medical occurrence observed in a subject that develops or worsens from Screening/Baseline, whether or not considered intervention related. An AE can be any unfavorable and unintended sign, symptom, or disease temporally associated with the use of an intervention and does not imply any judgment about causality.

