2.4 Safety Analysis

Safety analyses will be performed for the **Safety Subject Set**.

For the primary safety analysis, the number and percentage of subjects with major bleeding events within 72 hours of start of APT procedure will be reported with a 95% Wilson confidence interval.

Secondarily, the frequencies and proportions of subjects with technical procedural complications, symptomatic recurrent PE, and all cause mortality through the 365 day follow-up period will be reported with 95% Wilson score confidence intervals.

In addition, adverse events experienced through 30 days and SAEs through 365 days will be mapped to standard terms and summarized. For a given event, the frequency and proportion of subjects reporting it will be tabulated according to the worst severity experienced. Two separate tables will be constructed for each a) all reported events, b) events related to interventional procedure (not EKOS system), c) events related to EKOS system, d) events related to thrombolytic drug, e) events related to anticoagulant drug, f) bleeding events (3rd table will be constructed through 72 hours), and g) SAEs.

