At select participating sites: In addition to the vital signs specified in Section 7.4, bedside vital signs including, systolic/diastolic blood pressure, heart rate, respiratory rate, capillary refill time and SpO2 will be recorded at the start of the APT Procedure, and at each 30 minute interval until 4 hours post-completion of the APT Procedure. Along with the echocardiograms specified in Section 7.7, limited echocardiograms performed at the bedside for RV/LV ratio measurements will be obtained hourly after the start of the APT Procedure through 4 hours post procedure.

Scatterplots of RV/LV ratio (y-axis) vs vital sign measures (x-axis) and of change in RV/LV ratio vs changes in vital sign measures will be presented to assess the correlation of change in clinical parameters (vital signs) with change in markers of RV strain (RV/LV ratio), and associated Pearson or Spearman correlation coefficients, where applicable.

Subject Set = Safety Subject Set for (19 – 23)

- 21) Major Bleeding Events within 72 hours of initiation of APT*
- 22) Technical Procedural Complications (*captured on the EkoSonic Device CRF as “Was this device successfully placed and used for treatment?”; make this a by-patient listing*)
- 23) Symptomatic Recurrent PE and Symptomatic Recurrent PE up to Day 365 (Confirmed by imaging)
- 24) All cause mortality up to Day 30 and all cause mortality up to Day 365 (*note: per AE and study exit CRFs*)
- 25) Adverse Events (*Run tables for AEs up to Day 30: AE start date ≤ Date of 30 Day Follow Up Visit per Follow-Up CRF*)
 - a) All reported events
 - b) Related to interventional procedure (not EKOS system)
 - c) Related to EKOS system
 - d) Related to thrombolytic drug
 - e) Related to anticoagulant drug
 - f) Bleeding events (*all site reported bleeding events, make tables for:*
-All reported bleeding events
-Those within 72 hours of APT start
-Those related to:
-interventional procedure (not EKOS system)
-EKOS system
-thrombolytic drug
-anticoagulant drug
 - g) SAEs

Also run analyses for (g) through Day 365, including those through 30 days.

26) Freedom from major harm occurring between enrolment and 30 days and assessed by the Safety Monitor using the following criteria:

- a. Mortality – all cause and PE related
- b. CV collapse: Defined as one or more of the following:
 - i. >40mmHg drop in SBP (for >15 minutes from documented blood pressure as an in-patient) despite IV fluid challenge and absence of new atrial arrhythmia.

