Appendix 2: Derivations

2.6 Imputation rules

2.6.1 AE date imputation

The following algorithm should be used to estimate start dates for which only partial information is known:

- Missing day and month
 - If the year is the same as the year of first study treatment, then the day and month of the start date of treatment will be assigned to the missing fields
 - If the year is prior to the year of first study treatment, then December 31 will be assigned to missing fields
 - If the year is after the year of first study treatment, then January 1 will be assigned to the missing fields
- Missing month only
 - Treat day as missing and replace both month and day accordingly to the procedure above
- Missing day only
 - If the month and year are the same as the year and month of first study treatment, then the start date of treatment will be assigned to the missing day
 - If the month and year are before the year and month of first study treatment, then the last day of the month will be assigned to the missing day
 - If the month and year are after the year and month of the first study treatment, then the first day of the month will be assigned to the missing day

If the imputed start date result is after the stop date (and the stop date is complete), the imputed start date will be reset to the stop date.

The following algorithm should be used to estimate stop dates for which only partial information is known:

- Missing year
 - Date left missing
- Missing month
 - Impose “December”
- Missing day

- Impute last day of that month

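### The adverse event tables in SAP item 25 have an upper date limit but no lower one, so the descriptive by-arm tables can include events that began before the procedure

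*SAP*

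**What the plan says.** **Selection of events.** SAP Appendix 1, item 25 gives the rule "Run tables for AEs up to Day 30: AE start date ≤ Date of 30 Day Follow Up Visit per Follow-Up CRF". SAP 2.4 says that "adverse events experienced through 30 days and SAEs through 365 days will be mapped to standard terms and summarized". Both set the end of the period only.

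**Recording of events.** Protocol 8.1 defines an adverse event as "any untoward medical occurrence observed in a subject that develops or worsens from Screening/Baseline, whether or not considered intervention related". Protocol 6.6 requires that, at 72 hours or discharge, "all Adverse/VTE/Bleeding Events that occurred from Screening/Baseline will be recorded in the eCRF".

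**The time before the procedure.** Protocol 6.3.2 has treatment "started within 48 hours from the Screening/Baseline CTA evaluation", and the schedule of assessments allows screening up to 48 hours before APT start. Protocol 6.3.1 states that "All study subjects will continue on the anticoagulant medication initiated prior to enrollment in the trial".

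**Imputation.** SAP Appendix 2, 2.6.1 has separate rules for start dates before, during and after the month or year of first study treatment. For an event in the treatment month with an unknown day, "then the start date of treatment will be assigned to the missing day".

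**The concern.** The trial compares regimens that differ in r-tPA rate, total dose and ultrasound duration. An event that began before venous access or infusion says nothing about any of these. Under the item 25 rule, it still counts in the arm's incidence if the patient went on to have the procedure.

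The patients are anticoagulated in the hours before the procedure, so minor bleeding is a plausible example. A reader of a by-arm table of all reported bleeds would normally take it to describe what followed treatment. In small arms, one or two earlier events could change the impression that the table gives.

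**Working it through.** The plan states no figure on this point, so the check is mainly one of text.

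1. **Is there a lower limit on events?** Not in SAP 2.4, and not in item 25 for its general tables. Neither document defines treatment-emergent events.

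2. **Do earlier events reach the database?** Yes. The schedule of assessments has no adverse event mark in the Screening/Baseline column, but the collection at 72 hours or discharge in Protocol 6.6 looks back to Screening/Baseline. The definition in Protocol 8.1 uses the same reference point.

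3. **Does the analysis set remove them?** No. The Safety Subject Set in SAP 2.1 selects subjects in whom the procedure was initiated. It does not select events by date, so a treated subject brings all recorded events into the tables.

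4. **Which tables are exposed?**

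| Table | Lower limit stated? | Can a pre-procedure event enter? |
|---|---|---|
| 25a all events | No | Yes |
| 25b–d procedure-, EKOS- and thrombolytic-related | No | Only if so attributed |
| 25e anticoagulant-related | No | Yes |
| 25f all bleeds; anticoagulant-related bleeds | No | Yes |
| 25f bleeds within 72 hours of APT start | Yes | Only through imputation |
| 25g SAEs, to Day 30 and Day 365 | No | Yes |
| Item 21 major bleeds and primary safety endpoint | Yes, APT initiation | Only through imputation |
| Item 26 freedom from major harm | Yes, enrolment | Yes, by its own definition |

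5. **How does imputation act?** A bleed the day before the procedure, in the same month and with the day missing, is given the treatment start date. It can then fall inside a 72-hour window to which it does not belong.

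6. **Scale.** SAP synopsis: 29 UK subjects enrolled in 3 arms. Arm sizes are not given. Assuming an even split, 29/3 = 9.7, or about 10 per arm. Item 25 carries no asterisk, so under the heading of Appendix 1 it is run for the UK Extension alone.
   - One patient whose only event was before the procedure adds 1/10 = 10 percentage points (1/9 = 11.1 points in an arm of 9).
   - The Wilson 95% interval is (p + z²/2n ± z√[p(1−p)/n + z²/4n²]) / (1 + z²/n), with z = 1.96. For 0/10 it is 0 to 27.8%. For 1/10 it is 1.8 to 40.4%.
   - At the planned 25 per arm the step would have been 1/25 = 4 points, from 0% (0 to 13.3%) to 4% (0.7 to 19.5%).

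   The SAP does not ask for intervals on the item 25 tables; they are shown only for scale. They overlap heavily, so one such event changes the displayed rate but would not by itself separate two arms.

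**The case against.** The case for leaving the plan as it is has several parts.

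- **The tables follow the protocol's own definition.** Protocol 8.1 counts events from Screening/Baseline whatever their cause, and the exposed tables are titled as all reported events. Nothing is contradicted. This stands: the point concerns how useful the tables are and how they will be read.
- **The outcomes that carry the safety conclusion are already anchored.** A reader might infer that no table separates events before and after the procedure, or that the primary safety result is inflated. The documents do not support that. The primary safety endpoint, item 21 and the 72-hour bleeding table all start at APT initiation. Only the imputation route in step 5 remains.
- **Attribution is tabulated separately.** A reader might also infer that bleeds on heparin are charged to the assigned regimen. Protocol 10.1 analyses safety by actual treatment received, and a bleed on anticoagulant before access would reach the thrombolytic, EKOS or procedure tables only if it were misattributed. This stands.
- **Such events should be rare and not directed to one arm.** The window is at most 48 hours. Recent or active major-organ bleeding and high risk of catastrophic bleeding are exclusions. Arms are randomised, and no between-arm test of adverse events is planned. This stands, and it rules out a claim of systematic bias between regimens. It does not prevent chance imbalance in arms of about 10.
- **Any error overstates event rates.** That is conservative for a single arm, but it does not help when arms are read side by side.
- **A cut at venous access needs clock times.** Item 25 works with start dates, and the documents list time of onset only among the items for expedited SAE reports (Protocol 8.12). This stands and limits what the fix can achieve.

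**Conclusion.** The gap is real and limited. As written, the descriptive by-arm tables 25a, 25e, 25f (all reported and anticoagulant-related bleeds) and 25g, including the Day-365 SAE table, can include events that began before the procedure. The documents do not show that any such event occurred, how often one would, or that regimens would be affected unequally.

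The figure of about 10 percentage points is the effect of one affected patient in an arm of about 10. It rests on an assumed even split of 29 enrolled subjects and is not an estimate of the expected distortion. The change is worth making because it alters what the tables count and costs little. It does not call the primary safety analysis into question.

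**What to change.** In SAP 2.4 and item 25:

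- Limit tables 25a to 25g, including the Day-365 SAE table, to events with onset or recorded worsening at or after the start of EkoSonic placement. SAP 2.1 already names the variable (EXSTTM). Using placement rather than the start of infusion keeps access-site bleeds in the tables. Leave the 72-hour bleeding table anchored to APT start.
- Use clock time where it was recorded. Keep events on the procedure date that have no time, or that have an imputed date, in the tables as the conservative choice, and flag imputed dates.
- List events from Screening/Baseline to the start of placement separately, by arm.
- State that arms in the safety tables are by actual treatment received, as in Protocol 10.1. The SAP says only that analyses are by treatment arm.

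Item 26 can stay as it is, since its period is defined from enrolment.

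The cost is a few lines of SAP text and one extra listing, with no new data collection. The downside is that some same-day events from before the procedure cannot be separated where no time was recorded, and worsening can be used only where its date was captured.

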Appendix 2: Derivations

2.6 Imputation rules

2.6.1 AE date imputation

The following algorithm should be used to estimate start dates for which only partial information is known:

- Missing day and month
 - If the year is the same as the year of first study treatment, then the day and month of the start date of treatment will be assigned to the missing fields
 - If the year is prior to the year of first study treatment, then December 31 will be assigned to missing fields
 - If the year is after the year of first study treatment, then January 1 will be assigned to the missing fields
- Missing month only
 - Treat day as missing and replace both month and day accordingly to the procedure above
- Missing day only
 - If the month and year are the same as the year and month of first study treatment, then the start date of treatment will be assigned to the missing day
 - If the month and year are before the year and month of first study treatment, then the last day of the month will be assigned to the missing day
 - If the month and year are after the year and month of the first study treatment, then the first day of the month will be assigned to the missing day

If the imputed start date result is after the stop date (and the stop date is complete), the imputed start date will be reset to the stop date.

The following algorithm should be used to estimate stop dates for which only partial information is known:

- Missing year
 - Date left missing
- Missing month
 - Impose “December”
- Missing day

- Impute last day of that month

2.7 EQ-5D-5L Derivations³

Question	Text	Coded Value
Mobility	No problems/No pain/Not anxious	1
Self-Care	Slight problems/Slight pain/Slightly anxious	2
Usual Activities	Moderate problems/Moderate pain/Moderately anxious	3
Pain/Discomfort	Severe problems/Severe pain/Severely anxious	4
Anxiety/Depression	Unable/Extreme Pain/Extremely anxious	5

The following table will be used in calculating the index value from the 5-digit health state.

Index value = $1 - (Dimension\ 1\ Estimate + Dimension\ 2\ Estimate + Dimension\ 3\ Estimate + Dimension\ 4\ Estimate + Dimension\ 5\ Estimate)$

The dimension estimates will be taken from the table below. Each estimate corresponds to the level each respondent checked for each dimension. For example, if a patient has a health state of 23245, the following calculation will be used:

$$1 - (0.058 + 0.080 + 0.050 + 0.276 + 0.289) = 0.247$$

Constant		1.000
Mobility	None	0
	Slight	0.058
	Moderate	0.076
	Severe	0.207
	Unable	0.274
Self-care	None	0
	Slight	0.050
	Moderate	0.080
	Severe	0.164
	Unable	0.203
Usual Activities	None	0
	Slight	0.050
	Moderate	0.063
	Severe	0.162

	Unable	0.184
Pain/discomfort	None	0
	Slight	0.063
	Moderate	0.084
	Severe	0.276
	Unable	0.335
Anxiety/depression	None	0
	Slight	0.078
	Moderate	0.104
	Severe	0.285
	Unable	0.289

References

¹ Fasullo S, Scalzo S, Maringhini G, et al. Six-month echocardiographic study in patients with submassive pulmonary embolism and right ventricle dysfunction: comparison of thrombolysis with heparin. Am J Med Sci. 2011;341: 33-39

² Hochberg, Y, A Sharper Bonferroni Procedure for Multiple Tests of Significance, Biometrika 75, 800 2, 1988

³ Devlin N et al. Valuing Health-Related Quality of Life: An EQ-5D-5L Value Set for England. EuroQol Research Foundation. 2016.
